Methods: The study will be conducted as a placebo-controlled, triple-blind, randomized trial. It will consist of a 4-week intervention followed by a 4-week follow-up period. The target sample size is 20 patients with moderate asthma aged 18 to 60 years. Eligible participants will be randomly assigned to either the experimental group or the control group in equal numbers. Patients in the experimental group will take Glasthma syrup (7.5 mL, twice a day), while patients in the control group will take a matching placebo. Both groups will receive a 4-week combination of a long-acting beta2 agonist and a leukotriene modulator as standard of care. Inhaled corticosteroids can be used as rescue medication as needed.

Results: The primary outcomes are asthma symptom scale, lung function, and intestinal permeability. Secondary outcomes include quality of life, symptom recurrence rates, and blood tests. A safety assessment will also be conducted during the trial.

Conclusion: In this trial, the effects of Glasthma syrup in patients with moderate asthma will be examined. The study will also assess the effects of the formulation on the gut-lung axis by simultaneously monitoring the gut permeability index, asthma symptoms, and lung function.

Keywords: bronchial asthma, persian medicine, intestinal permeability, clinical trial

INTRODUCTION

In Persian medicine, the treatment of asthma with herbs has been mentioned in various formulas [1]. Despite the rich variety of medicinal preparations in Persian medicine, there has been limited research on their effectiveness and possible

adverse effects [2-6]. Considering the increasing popularity of herbal and traditional remedies, it is necessary to evaluate the performance of these herbal therapeutic formulations and their side effects [7].

Asthma is a chronic disease, and multiple medications have been developed to reduce inflammation of the airways and con-

tract the smooth muscles of walls.

Common drugs for asthma contain, as active ingredients, medicinal plants mentioned in some traditional medicine recipes [8]. Physiologic effects such plants varies depending on the composition of each formulation.

This complexity is not fully understood, but empirical evidence suggests that they have a measurable effect on mucus accumulation, improve bronchial relaxation, and reduce airway inflammation [9].

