This is a single-center randomized triple-blind controlled trial. The trial was authorized at the Medical University of Mashhad, Iran (code: 991551), approved by the Iranian National Biomedical Research Ethics Committee, code IR.MUMS.REC.1400.076, and registered with the Iranian Clinical Trials Registry.

The goal of the trial is to analyze the effect of Glasthma syrup, compared with placebo, on respiratory symptoms, pulmonary function test results, and gut permeability index (lactulose/mannitol ratio) in patients with moderate asthma. This study complies with the Standard Protocol Item: Guidelines for Interventional Trials (SPIRIT) Recommendations (Table 1).

2. Trial procedure

The complete trial includes a screening assessment, a 1-week run-in period, a 4-week treatment period (weeks 1 to 4), and a 4-week follow-up period (weeks 5 to 8) (Fig. 1).

First, patients with asthma who met the inclusion criteria will be invited to participate in the study. They will be given the necessary explanations about the study conditions, and if they agree, after signing a written consent form, an asthma registry questionnaire will be completed [28]. The patients will have a complete blood count (CBC), liver and kidney function tests, total serum IgE test, pulmonary function test (PEF), urine analysis, creatinine clearance (ClCr), and a 5-hour urine L:M test.

After the baseline assessment, participants will be randomly assigned to receive Glasthma syrup or placebo syrup for 4 weeks. Symptom severity and quality of life will be self-assessed by participants and recorded weekly throughout the treatment period. Face-to-face blind assessments will be scheduled for the end of the fourth week. Patients in both groups will have virtual follow-up visits during the intervention and 4 weeks later to be informed on the medication use and possible side effects.

Assessments of symptoms and quality of life, as well as all blood, urine, and lung tests, will be repeated at the end of the 4-week intervention. After the intervention period, a 4-week

Table 1. Schedule of enrolment, interventions, and assessments

Time point	Study period								
	Allocation		Post Allocation				Close up		
	T0	T1	T2	T3	T4	T5	T6	T7	T8
Enrollment									
Eligibility screen	*								
Inform consent	*								
Medical history and physical examination	*								
Allocation	*								
Intervention Glasthma/control		*	*	*	*				
Assessment									
Baseline survey	*								
Asthma severity	*	*	*	*	*	*			

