Quality of life	*	*	*	*	*	*			
Lung function	*						*		
L:M in urine	*						*		
Blood tests	*						*		
Rate of symptom relapse							*	*	*
Health resource utilization data	*	*	*	*	*				
Safety		*	*	*	*				
Follow up							*	*	*
End line survey									*

follow-up period will follow. During these 4 weeks, patients will continue the standard treatment, with weekly recordings of symptom severity and quality of life scores, as well as the need for rescue medication.

Participants will be recruited by a pulmonologist and clinical allergist from the Respiratory Clinic at Ghaem Hospital in Mashhad. Classified online posters and advertisements will also be used to inform and engage patients. Inclusion criteria are a history of asthma over 6 months and an FEV1 of 60-80%.

Patients with one or more of the following conditions will be excluded: cognitive diseases, history of seizure disorder, use of oral or systemic corticosteroids, pregnancy or lactation, allergy to nuts, need for hospitalization for any reason, smoking, exacerbation of the disorder at the start of the study, high blood pressure or diabetes, and concurrent participation in other trials or participation in a trial in the previous month.

3. Interventions

Patients in the intervention group will be instructed to receive 7.5 mL of Glasthma syrup twice daily for 4 weeks in

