be sufficient to achieve statistical and clinical significance. According to the L:M literature [29], a sample size of 5 patients was obtained: with an expected loss of 20%, 7 patients were selected. The sample size obtained based on FEV1 [30] and ACQ7 questionnaire [31] was also the same. Hence, a sample size of 7 participants in each group corresponds to a statistical power of 90%, ignoring 0.05 bilateral type I error, to detect a difference of 2.5 in this experiment with p-values less than 0.05 indicating statistical significance. We increased the sample size to 10 participants per group taking into account a 20% loss for follow-up and other potential losses related to non-compliance and quality control.

Researchers will attend a training session to prepare for their role. Each will be given a copy of the workflow and asked to commit to the protocol. The training will provide information on registration process and assessment of quality of life. PEF and blood tests and urinalysis will be performed by relevant specialists.

The data will be collected in a report file and entered into a pre-designed statistical software form. During the trial period, data will be entered and recorded twice by two different users, and any changes made on the data will be recorded and dated on the relevant forms. Two qualified people will check the quality of the data regularly. Data review and monitoring during the project will be performed by an independent supervisor other than the project sponsor or researcher. It is the responsibility of the Mashhad Medical University to monitor the data and the trial process and, if necessary, decide to terminate the study early.

RESULTS

1. Outcomes

Based on previous studies, the changes in patients' clinical symptoms and evaluation of lung function and intestinal permeability from the beginning to the end of the follow-up period were selected as the primary outcome of the research design.

The Asthma Control Questionnaire (ACQ) will also be used to assess the severity of the symptoms. The first five questions are about the symptoms of the disease. Question 6 examines the use of rescue drugs, and Question 7 examines the level of FEV1 in pre-bronchodilators. Each parameter is categorized from 0 (fully controlled) to 6 (fully uncontrolled). The minimum clinically significant difference is 0.5 [32].

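### The seven-question ACQ needs FEV1, but spirometry is repeated only once after baseline, so the score cannot be formed at seven of the eight weekly recordings, including the end of follow-up

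*Protocol*

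**What the plan says.** **Outcome.** The Abstract states: "The primary outcomes are asthma symptom scale, lung function, and intestinal permeability". Results, 1. Outcomes sets the time frame: changes "from the beginning to the end of the follow-up period were selected as the primary outcome of the research design". The same section names the instrument: "The Asthma Control Questionnaire (ACQ) will also be used to assess the severity of the symptoms". It describes seven questions, each rated 0 to 6: five on symptoms, a sixth on rescue drug use, and a last one of which it says "Question 7 examines the level of FEV1 in pre-bronchodilators". It gives 0.5 as the smallest clinically significant difference. No other symptom scale is described.

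**Sizing.** Materials and Methods, 5. Sample size refers to the seven-question form: "The sample size obtained based on FEV1 [30] and ACQ7 questionnaire [31] was also the same".

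**Schedule.** Materials and Methods, 2. Trial procedure states: "Symptom severity and quality of life will be self-assessed by participants and recorded weekly throughout the treatment period". Weekly recording of symptom severity continues through the four follow-up weeks. All lung tests are repeated at the end of the four-week intervention. That is also the only face-to-face assessment scheduled after baseline; the other follow-up contacts described are virtual. In Table 1, asthma severity is marked at T0 to T5, and the row "Lung function" at T0 and T6.

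**Analysis.** Results, 3. Statistical analysis compares the arms on change from baseline to any time point, and uses paired t-tests within each arm.

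**The concern.** A patient can answer the symptom and rescue questions at home, but the FEV1 question needs spirometry. The protocol plans weekly symptom scores and an end-of-follow-up primary change, yet it schedules only one spirometry after baseline. It defines no shorter ACQ score, mentions no home spirometry and gives no rule for a missing question 7.

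At most recordings the analyst would have to drop question 7, so that baseline and later scores are made of different items, or carry an earlier FEV1 forward, so that one item cannot reflect any change since then. Either way, the change from baseline would not be the quantity the protocol describes. This affects the end of follow-up, which the protocol itself names as the end of the primary time frame.

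**Working it through.** The protocol gives no figure of its own to reproduce here. The check sets the questionnaire against the schedule.

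**Inputs**
- Items in the score: 7, one of them FEV1 (Results, 1. Outcomes).
- Weekly symptom recordings after baseline: 4 in treatment + 4 in follow-up = 8 (2. Trial procedure).
- Spirometry after baseline: 1, at the end of week 4 (2. Trial procedure).
- End of the primary time frame: end of follow-up, week 8 (Results, 1. Outcomes).

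**Count by the text**
- Recordings with question 7 available: baseline and week 4.
- Post-baseline recordings without it: 8 − 1 = 7, namely weeks 1, 2, 3, 5, 6, 7 and 8.

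**Sensitivity to the reading of the schedule**
- Table 1 taken literally: severity at T0 to T5 and lung function at T0 and T6 coincide only at T0, so no seven-question score exists after baseline. The table was read by a program and its columns may have shifted, so the conclusion does not rest on this.
- Wherever the single later lung test falls, it can serve at most one of the eight recordings, so at least 7 lack question 7.
- If the primary time frame is taken to imply a further spirometry at week 8, which neither the procedure text nor Table 1 schedules, 8 − 2 = 6 recordings still lack it.

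**Illustration only.** The protocol gives no scoring rule. Assume the score is the mean of its items. Let m be the mean of questions 1 to 6 and x the value of question 7.
- Seven-item score: (6m + x)/7. If question 7 is dropped later, the score moves by m − (6m + x)/7 = (m − x)/7 with no clinical change. An assumed gap of two categories gives 2/7 = 0.29, which is 0.29/0.5 = 57% of the stated threshold.
- If question 7 is held at baseline and all items would otherwise change by the same amount, the score shows 6/7 of that change and loses 1/7 (14%).

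The first effect enters a within-arm paired comparison directly. Between randomised arms it cancels in expectation, but not exactly in one trial with 10 patients per arm.

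**The case against.** **No sentence says that all seven questions are scored every week.** What is recorded weekly is symptom severity, and the protocol identifies the first five questions as the symptom questions. A weekly score from those is feasible. This is true, and it is the basis of the fix. But the protocol does not define such a score, describes no other symptom scale and sizes the trial on ACQ7. The word "also" in the ACQ sentence leaves only slight doubt that the ACQ is the primary scale.

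**Scoring and missing items belong in a statistical analysis plan, which is not shown.** This is right for the scoring rule, and its absence is not the complaint. The instrument, the recording times and the spirometry times are all fixed in the protocol, and they do not fit together.

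**The spirometry schedule is itself unclear.** The primary time frame covers lung function to the end of follow-up, and the Outcomes section speaks of FEV1 before and after drug withdrawal. This stands as a reason to reconcile the passages. No reading supplies a weekly FEV1.

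**Stronger readings that the protocol does not support**
- That no usable ACQ7 exists after baseline. By the text, it can be formed at baseline and at the end of week 4, and that comparison is intact.
- That FEV1 is wrongly counted twice because lung function is also primary. The overlap is inherent in a seven-question ACQ. It makes the two outcomes correlated, and the protocol does not pool them.
- That the relapse outcome is distorted. Relapse is never defined by the ACQ.
- That the description of rescue treatment invalidates question 6. The Abstract and 3. Interventions describe inhaled corticosteroids differently and must be reconciled, but that is a separate matter and has no bearing on whether the score can be formed.

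**Conclusion.** The point stands as a mismatch between the defined questionnaire and the schedule. By the text, the seven-question score is available at baseline and week 4 and unavailable at 7 of 8 weekly recordings, including week 8. The count rests on two readings: that the ACQ is the primary symptom scale, and that the end of week 4 is the only spirometry after baseline.

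The size of any distortion cannot be derived from the protocol. The 0.29-point and 14% figures are illustrations. They assume mean-of-items scoring and, respectively, a dropped question 7 with a two-category gap, or a frozen question 7 with equal movement of all items. The protocol states none of these. The change is worth making because it is specific and cheap, and because the gap reaches the stated end of the primary time frame.

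**What to change.** - Define the symptom outcome as the mean of ACQ questions 1 to 5, computed identically at baseline and at every weekly recording, follow-up included.
- Compute ACQ7 only at baseline and at the end of week 4, where spirometry exists, and label it as such.
- Correct Table 1 so that its timing of asthma severity and lung function agrees with 2. Trial procedure and with the time frame in the Outcomes section.

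**Cost.** There is no new procedure and no added patient burden, since the same questions are answered. The change does alter the score behind a primary outcome. The 0.5 threshold is given for the ACQ as described with seven questions, and the sizing cites ACQ7, so both apply to the five-question score only as stated assumptions. The protocol dates the start of recruitment to December 2021 and expects the last follow-up in April 2022, before the paper's acceptance in July 2022. The redefinition should therefore be dated, and made while the allocation codes are still closed.

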Lung function test with HI-801 multifunction spirometer, change in forced expiratory volume per second (FEV1), ratio of forced vital capacity captured by forced expiratory volume per second (FEV1/FVC) before and after drug withdrawal in the intervention and placebo groups will be examined.

To determine gut permeability, we will measure the ratio of mannitol in the 5-hour urine at the beginning and end of the intervention. In this method, non-metabolized sugar molecules in the quantity of 5 grams of lactulose and 2 grams of mannitol in the form of sachet will be used and the degree of permeability or malabsorption of the intestine will be determined by the amount of secretion of these two sugars in 5-hour urine by standard LC-MS/MS (6410 LC/MS/MS triple quadrupole). The standard required amount is diluted with 10 mm ammonium acetate phase in HPLC grade water: ACN (80:20), SIL column of 25 cm, injection volume of 10 μ L, flow rate of 0.6 mL/min. The negative status for lactulose is 341.2/161 or 341.2/101.1, while that for mannitol 181.1/101 or 181.1/89. The tests will be performed in a quality control laboratory.

As the secondary outcome, the patients' quality of life will be assessed using the Asthma Short Quality of Life Questionnaire (mini-AQLQ) at the beginning and end of the intervention [33]. This questionnaire comprising 15 questions will evaluate disease symptoms, environmental effects, patients' feelings, and limitations in patients' activity. For each question, the scores vary from 0 to 6; the lower the score, the lower the quality of life. The minimum clinically significant difference is 0.5 [34].

Laboratory tests to be performed include analysis of whole blood samples, total serum IgE levels, renal and liver function tests, urinalysis, and ClCr at the start and end of the intervention. In this study, patients will be excluded from the study if any disease is observed according to the test results at the start of admission. Changes in each dose are normally recorded to assess the efficacy or possible side effects of the drug.

In addition, other conditions, such as the need for hospitalization or emergency treatment and use of rescue medication, will also be recorded. If we notice symptoms of other diseases during the intervention, or if a patient requires an unforeseen medication, the patient will be excluded from the study, and the results will be recorded.

2. Safety assessment

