Liver and kidney function tests will be performed using blood and urine samples at the beginning and end of the inter-

vention. During the intervention, researchers will also follow up with patients, and any signs, symptoms, and unexpected feelings will be recorded, reported, and linked to the experimental drug.

Results, severity, time of onset, duration, duration of treatment, and follow-up of side effects will be recorded in the report form. All side effects will be assessed to examine the causal impact of the intervention according to the criteria established by the Iranian National Biomedical Research Ethics Committee.

Participants will be excluded from the study if they experience intolerable side effects, acute or persistent organic disease, new-onset disease, a need to take non-asthma medication, or patient dissatisfaction during the study period. The patients' withdrawal from the plan will be recorded stating the reasons for discontinuing the drug and the final date of its use.

Deleted and terminated projects will be analyzed in the final report. Withdrawal of the patient without any reason is acceptable and will not interfere with the continuation of the daily treatment of the patient.

The researchers will explain the results of the clinical and laboratory tests to the patients. Participants will be provided with ongoing support throughout the study, including free registration, medical consultation, and follow-up.

3. Statistical analysis

Data analysis will be performed by independent statistical experts using IBM Statistics 16.0 software. Quantitative data will be expressed as mean and standard deviation, or median and quadratic range. Dual data, such as symptom recurrence, will be shown as 95% hazard ratios and confidence intervals. A p-value less than 0.05 will be considered to indicate a statistically significant difference.

Basic characteristics will be described using standard statistical analysis methods. Continuous variables will be analyzed using t-tests, while classified variables will be analyzed using chi-square tests. The main analysis will include the treatment intent and the subject of each protocol for initial results. The latter prospective approach will be used in an intention-to-treat analysis to assign missing data.

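### Randomised patients are excluded from the study for events after randomisation, with no further outcome measurement and an unreadable missing-data rule, so the intention-to-treat result is open to bias

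*Protocol*

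**What the plan says.** Two rules in the protocol act after randomisation, and both remove the patient from the study rather than from the syrup.

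- Results, Safety assessment: "Participants will be excluded from the study if they experience intolerable side effects, acute or persistent organic disease, new-onset disease". The sentence continues with "a need to take non-asthma medication, or patient dissatisfaction during the study period".
- Results, Outcomes, on other illness or treatment arising during the intervention: "if a patient requires an unforeseen medication, the patient will be excluded from the study, and the results will be recorded".

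On what is kept for such patients, Safety assessment says that the "withdrawal from the plan will be recorded stating the reasons for discontinuing the drug and the final date of its use". It adds: "Deleted and terminated projects will be analyzed in the final report".

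Results, Statistical analysis names the analysis sets: "The main analysis will include the treatment intent and the subject of each protocol for initial results". I read this as intention-to-treat and per protocol. On missing values it says: "The latter prospective approach will be used in an intention-to-treat analysis to assign missing data".

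Gut permeability (L:M) is measured "in the 5-hour urine at the beginning and end of the intervention". Lung function is likewise measured at baseline and repeated at the end of the four treatment weeks (Trial procedure, and two marks in Table 1). Symptom severity is recorded weekly.

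**The concern.** An intention-to-treat analysis needs the outcome of everyone randomised, including those who stop treatment. Here stopping and leaving are the same event. The reasons for leaving are not neutral: side effects can depend on the arm, and dissatisfaction may follow lack of benefit. The end-of-treatment values of these patients are never collected, and no analysis plan can recover them later.

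The protocol then replaces them by a rule that names no recognisable method. For FEV1 and L:M, two of the three primary outcomes, there is no value between baseline and the end of treatment to draw on. If the rule means last observation carried forward, every patient excluded during treatment receives a change of exactly zero on both. With 10 patients per arm, a handful of such values can move the result.

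**Working it through.** **Step 1. How many patients the plan expects to lose.** The Sample size section inflates 5 per group for 20% loss: 5 / (1 − 0.2) = 6.25, rounded up to 7, which reproduces. It then goes from 7 to 10 for 20% loss and other losses; 7 / 0.8 = 8.75, or 9, so 10 includes a small further margin. Twenty per cent of 10 is 2 patients per arm, and I use 2 below. The protocol gives no SD, so all effects are in assumed SD units of the change score.

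**Step 2. The texts side by side.**

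| Question | What the protocol provides |
|---|---|
| Who leaves | Patients with side effects, new illness, other medication or dissatisfaction, after randomisation |
| What is recorded at withdrawal | Reason and last date of drug use |
| Outcome visits afterwards | None stated |
| Main analysis | Intention-to-treat and per protocol |
| Filling of missing values | One rule, not interpretable |

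**Step 3. If affected patients are dropped**, as a per-protocol analysis would do. Assume no true effect, 10 per arm, and the 2 worst outcomes leaving one arm only. The expected two lowest of 10 standard normal values are −1.54 and −1.00. Removing them shifts the mean of the remaining 8 by (1.54 + 1.00) / 8 = 0.32 SD. By simulation (t-test, 100,000 runs) the two-sided 5% error becomes 11.5%. With the worst 3 removed, the shift is 0.45 SD and the error 16.6%.

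**Step 4. If the same 2 patients get zero change.** This assumes that the rule means last observation carried forward. If both arms improve by m SD, the shift is (1.54 + 1.00 − 2m) / 10 = 0.254 − 0.2m.

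| Improvement m in both arms (SD) | Shift (SD) | Two-sided error |
|---|---|---|
| 0 | 0.25 | 10.2% |
| 0.5 | 0.15 | 6.3% |
| 0.7 | 0.11 | 5.1% |
| 1 | 0.05 | 3.9% |

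The direction can also reverse. If 2 random patients leave one arm while both arms improve by 1 SD, the shift is −(2/10) × 1 = −0.20 SD, and the error is 6.6%.

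**Step 5. Dilution of a real effect.** Assume a true effect of 1.5 SD and zero-change fill for 2 random patients in each arm. The treated mean is 0.8 × (m + 1.5) and the control mean 0.8 × m, so the estimate is 0.8 × 1.5 = 1.2 SD whatever m is. Simulated power is 76% at m = 0, 65% at m = 0.7 and 58% at m = 1. For comparison, 8 complete cases per arm give a noncentrality of 1.5 × √(8/2) = 3.00 with 14 degrees of freedom, power 80%. All 10 followed give 1.5 × √(10/2) = 3.35 with 18 degrees of freedom, power 89%.

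**The case against.** The strongest reply is that the protocol keeps excluded patients in the analysis. It names intention-to-treat, says that missing values will be assigned, and promises to analyse deleted cases in the final report. This stands in part. A reader might infer that these patients leave the intention-to-treat set, but no section says so, and the 11.5% and 16.6% error rates therefore describe dropping only. The reply does not supply the missing measurements, though: the promise gives no method and no follow-up.

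Other stronger readings also go beyond the text.

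- *The result is biased in favour of the syrup.* The documents do not fix who leaves, from which arm, or how much each arm improves. Patients and assessors are blinded, so under no effect dissatisfaction should arise in both arms. Losing exactly the worst patients from one arm is an upper-end case. Several triggers, such as non-asthma medication, need not mark poor asthma outcome, and rescue use and hospitalisation are to be recorded.
- *The rule is last observation carried forward.* This is a guess at a garbled sentence.
- *Filled values understate the variance.* This need not hold. With m = 0.7 and a 1.5 SD effect, the treated mean is 2.2 SD, and two zeros among ten raise that arm's expected variance from 1 to about 1.66.
- *Late adverse events are lost.* Safety assessment provides for recording the follow-up of side effects, and nothing ends this at exclusion.

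It may also be said that a separate analysis plan could define the missing-data method. It could, but the protocol already states a rule that cannot be applied, and whether patients are measured after stopping is trial conduct.

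**Conclusion.** The point holds in this form: the protocol equates several events after randomisation with leaving the study, provides for no outcome measurement afterwards, and assigns the missing values by an unreadable rule. The intention-to-treat result is open to bias; the protocol does not allow one to say that it is biased, or in which direction.

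The size is conditional. With 2 of 10 patients in one arm affected and no true effect, the error ranges from 3.9% to 11.5%, depending on the handling and the background improvement. With 2 random patients per arm given zero change, a 1.5 SD effect shrinks by one fifth, and power falls 13 to 31 percentage points below the 89% available if everyone were followed. The SD units, the 1.5 SD effect, the improvement of 0 to 1 SD, the choice of who leaves and the carry-forward reading are all assumptions.

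**What to change.** - Leave the clinical criteria for stopping syrup unchanged; they are not judged here. State in both the Outcomes and Safety assessment sections that stopping syrup is not leaving the study, and that a patient leaves only by withdrawing consent.
- Collect the scheduled ACQ, the week-4 FEV1 and L:M, and adverse events from every randomised patient who still consents.
- Analyse all patients as randomised.
- Replace the missing-data sentence with a defined method: a likelihood-based repeated-measures model for ACQ, and multiple imputation using baseline and arm for FEV1 and L:M. Treat per protocol as a sensitivity analysis.

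The cost is wording, plus following a few patients at visits that already exist. The downside is that some values will be recorded off syrup or under other medication. By the dates in the Recruitment section, follow-up may already be complete. The analysis changes would then still apply, and the report should show how many patients were excluded in each arm, when and why.
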